13 PROTOCOL VIOLATIONS

A protocol violation occurs when the subject or investigator fails to adhere to significant protocol requirements affecting the inclusion, exclusion, subject safety and primary endpoint criteria. Protocol violations for this study include, but are not limited to, the following:

- Early termination of temperature management protocol
- Removal of ECD prior to the end of surgery
- Failure to pack the right kidney with ice
- Inability to maintain target temperature for ≥ 1 hour
- Failure to meet inclusion/exclusion criteria
- Failure to comply with Good Clinical Practice (GCP) guidelines will also result in a protocol violation.

Protocol violations will be accounted for by intention-to-treat analysis. Withdrawal of the subject will not be required, as all study procedures are completed within the first visit at the time of LTx.

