RATIONALE	Patients undergoing liver transplantation (LTx) are at extremely high risk of perioperative acute kidney injury (AKI). AKI has enormous impact on outcomes and cost after LTx. 68% of patients at UCSF sustain some degree of AKI and 12% develop AKI Stage 3 (a three- fold increase in sCr from baseline or need for dialysis) after LTx. Thirty-day and 1-year mortality, graft survival, and progression to chronic kidney disease correlate with the presence and severity of AKI. Clearly, any intervention that reduces the incidence or severity of AKI in this population would have tremendous impact on short and long-term outcomes and cost. This trial will study mild hypothermia in LTx for prevention of AKI. The protocol is based on strong preliminary data from rodent studies showing that hypothermia protects renal function in ischemia- reperfusion models. Recent work from our department has shown that mild hypothermia in deceased organ donors improves graft function after kidney transplantation. In light of these preliminary data, we propose a trial of mild hypothermia to prevent AKI in LTx.	
STUDY DESIGN	This is a single-blind, randomized controlled trial	
PRIMARY OBJECTIVE	Assess whether or not mild hypothermia has a protective effect on early AKI after liver transplantation.	
SECONDARY OBJECTIVES	 Demonstrate the feasibility of mild hypothermia during liver transplantation. Assess whether or not mild hypothermia reduces early biomarkers of AKI during liver transplantation such as neutrophil gelatinase-associated lipocalin (NGAL) 	
NUMBER OF SUBJECTS	230	
SUBJECT SELECTION CRITERIA	Inclusion Criteria: 1. Age ≥ 18 years 2. LTx from a donor after neurologic determination of death (DNDD) Exclusion Criteria: 1. LTx from a donor after cardiac death (DCD) 2. LTx for acute liver failure (ALF) 3. Living-donor LTx 4. Simultaneous liver-kidney transplantation	

	5. Preoperative renal replacement therapy (RRT)	
	6. Preoperative intubation and/or mechanical ventilation	
	7. Portopulmonary hypertension	
TEST TREATMENT	Mild hypothermia (34-35 °C) during liver transplantation	
AND METHOD OF		
ADMINISTRATION	Mild hypothermia will be induced using an esophageal cooling device	
	(ECD), as well as standard measures after the induction of general	
	anesthesia until blood flow is completely restored to the liver. The	
	anticipated median duration of mild hypothermia will be 4-5 hours.	
	When feasible, the right kidney will also be packed with ice-cold	

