3.2 Secondary Objectives

The secondary objectives are:

• Assess the feasibility of a mild hypothermia protocol during LTx. Cooling will be performed using an ECD as well as standard measures. When possible, the surgeon will also apply local cooling (ice-cold sponges on the surgical field) to the right kidney during the anhepatic phase of the operation. After blood flow is fully

restored to the liver, the ECD and standard measures will be used to actively rewarm subjects. Feasibility will be assessed by the proportion of patients successfully completing the protocol, and the percentage of time spent within the target temperature range.

 Measure biomarkers of AKI during and after mild hypothermia or normothermia in LTx. NGAL, a protein elevated in AKI,³⁵ has been described by [name] group as an early biomarker of AKI during LTx.²⁴ Serum NGAL indicates glomerular injury, while urine NGAL is a marker of distal tubular injury.³⁶ Blood and urine samples will be collected for NGAL determination at baseline and two hours after reperfusion of the portal vein.

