8.3 Formulation of Test and Control Treatments

After induction of general anesthesia, the ECD will be connected to the Gaymar Medi-Therm III Hyper/Hypothermia Machine and tested for leaks according to the manufacturer's instructions. Then, it will be lubricated and placed into the esophagus of the subject in a manner identical to that of the standard OG tube used in LTx surgery.

The standard bladder temperature probe used in LTx operations will be connected to the PATIENT PROBE jack of the Gaymar Medi-Therm III, which will be used in AUTO/Rapid mode.

In both Study Arms (Mild Hypothermia and Normothermia), the subject will be given 2 grams of magnesium (Mg) sulfate IV at the beginning of surgery if the preoperative Mg < 2 mg/dL. This will be done because mild hypothermia may trigger a cold-induced diuresis and loss of electrolytes. Therefore, efforts will be made to keep the Mg normal (1.8-2.4 mg/dL) in both groups. Potassium will also be monitored carefully during surgery and replaced at the discretion of the attending anesthesiologist/study doctor.

Experimental treatment – Mild hypothermia (34-35 °C).

- Cooling will be initiated after induction of anesthesia and maintained throughout the anhepatic phase of LTx (Fig. 1). This will be done by selecting a Set Point temperature of 34.8 °C¹ on the Gaymar Medi-Therm III.
- In all feasible cases the surgeon will cover the peritoneal surface over the right kidney, which is exposed during the operation, with ice-cold sponges (lap sponges soaked in ice water and wrapped around ice cubes) to enhance cooling of the renal parenchyma. Local cooling will be applied to the right kidney beginning approximately 10 minutes prior to the anhepatic phase. The anhepatic phase is defined as application of the inferior vena cava (IVC) clamp and removal of the recipient liver.
- After the portal vein is reperfused, the ECD (by selecting a Set Point temperature of 37 °C on the Gaymar Medi-Therm III) and other standard measures (forced-air, fluid, and table warmers, plus a heated anesthesia circuit) will be used to actively re-warm the patient (expected warming rate ≥ 1 °C/hour). The goal is to achieve normothermia by case end.

Control – Normothermia (36.5-37.5 °C).

• After induction of anesthesia, the ECD (by selecting a Set Point temperature of 37 °C on the Gaymar Medi-Therm III) and standard warming measures will be used to maintain normothermia throughout the operation.

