15.3 Analysis of Primary Endpoint

Both intention-to-treat (ITT) and per-protocol analysis will be performed. All randomized, non-withdrawn patients will be included in the ITT analysis. All subjects completing the systemic temperature regulation protocol as outlined in Section 8.3 will be included in the per-protocol analysis. Subjects who had a protocol violation will be excluded from the per-protocol analysis.

The primary outcome (presence or absence of AKI) will be compared between the two arms by two-sample proportion test, furthermore, a multiple logistic regression model will be utilized where AKI status (present or absence) is considered as the outcome and arms along with demographic characteristics (e.g, race, gender, age, etc.) and clinical characteristics (such as local cooling, Model for End-Stage Liver Disease score, etiology of liver disease, etc.) are considered as predictors and/or covariates.

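### Right-kidney packing is required only where feasible, yet any failure to pack is a listed violation, so the per-protocol set for the primary endpoint is not uniquely defined

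*Combined protocol and SAP*

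**What the plan says.** Local cooling of the right kidney belongs to the experimental treatment and is conditional wherever that treatment is described:

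- Synopsis, test treatment: "When feasible, the right kidney will also be packed with ice-cold" sponges.
- Section 3.2: "When possible, the surgeon will also apply local cooling (ice-cold sponges on the surgical field) to the right kidney".
- Section 8.3, and in the same sense Section 4.1: "In all feasible cases the surgeon will cover the peritoneal surface over the right kidney".

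Section 13 lists among the protocol violations "Failure to pack the right kidney with ice". The item has no feasibility qualifier and is not limited to one arm. Section 13 also says that violations are handled through the intention-to-treat analysis.

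Section 15.3 plans a per-protocol analysis of the primary endpoint and defines its population in two consecutive sentences: "All subjects completing the systemic temperature regulation protocol as outlined in Section 8.3 will be included in the per-protocol analysis", then "Subjects who had a protocol violation will be excluded from the per-protocol analysis". The same section lists, as possible predictors in the logistic model, "clinical characteristics (such as local cooling, Model for End-Stage Liver Disease score" and others.

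On feasibility, Section 3.2 states: "Feasibility will be assessed by the proportion of patients" who complete the protocol, together with the percentage of time in the target temperature range. It does not define completion.

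**The concern.** A hypothermia patient whose kidney cannot be packed has been treated as Section 8.3 describes, yet Section 13 records a violation. Section 15.3 then gives opposite instructions for that patient. Two analysts following the text could build different per-protocol sets from the same data, and the choice might be made after outcomes are known.

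The exclusion route also raises a question of bias. Packing has no counterpart in the control arm, so this criterion can sensibly remove only hypothermia patients. Whether to pack is settled during the operation, after randomisation, by a surgeon who applies the ice and so must know the arm. If patients who cannot be packed differ in AKI risk from those who can, removing them from one arm while their counterparts stay in the other shifts the comparison without any treatment effect.

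The completion proportion in Section 3.2 has a related gap: it takes different values depending on whether packing counts towards completion.

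**Working it through.** **The rules applied to one patient.** Take a hypothermia patient who completed systemic cooling and rewarming as planned but could not be packed.

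| Place | Result |
|---|---|
| Section 8.3 | Treated as described |
| Section 13 | Protocol violation |
| Section 15.3, inclusion sentence | In the per-protocol set |
| Section 15.3, exclusion sentence | Out of the per-protocol set |
| Section 15.3, logistic model | Local cooling is expected to vary |

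The last row favours inclusion. If unpacked hypothermia patients were excluded, everyone left in that arm would be packed and no control would be. Local cooling would then coincide with arm, and a model containing both could not be estimated in that set.

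**The plan's own figure.** Section 15.6 gives 68% AKI, a 30% reduction, 80% power, two-sided overall alpha 0.05 and 101 per arm. Read as relative, the reduction gives 0.68 × 0.70 = 0.476, a difference of 0.204.

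- The two-proportion formula with pooled variance under the null is n = [1.960 × √(2 × 0.578 × 0.422) + 0.842 × √(0.68 × 0.32 + 0.476 × 0.524)]² / 0.204² = 90.8.
- With continuity correction, (90.8/4) × [1 + √(1 + 4/(90.8 × 0.204))]² = 100.4, which rounds up to 101.

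The stated figure is reproduced, and also at the final alpha of 0.0492. It does not depend on the per-protocol rule.

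**Shift if unpacked patients are excluded.** Assume no treatment effect, so that AKI is 68% overall in both arms. Let f be the share of the hypothermia arm not packed, and d their AKI risk minus the risk of packed patients. The overall rate is f(p + d) + (1 − f)p = 0.68, where p is the rate in packed patients. Hence p = 0.68 − f × d, and the shift is −f × d.

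The documents give neither f nor d, so the values below are assumptions. With 101 controls and n = 101 × (1 − f) hypothermia patients, SE = √(0.68 × 0.32/101 + p(1 − p)/n). The chance of a two-sided p value below 0.0492 is Φ(x − 1.967) + Φ(−x − 1.967), with x = f × d/SE.

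| f | d (points) | Per-protocol hypothermia rate | Shift (points) | n | Rejection under no effect |
|---|---|---|---|---|---|
| 20% | 0 | 68% | 0 | 81 | 4.9% |
| 10% | 10 | 67% | −1 | 91 | 5.2% |
| 20% | 20 | 64% | −4 | 81 | 8.6% |
| 30% | 20 | 62% | −6 | 71 | 12.7% |
| 20% | −20 | 72% | +4 | 81 | 8.9% |

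With d = 0 the only cost is precision. At the design effect, alpha 0.0492 and no continuity correction, power is 83.9% with 101 against 101 and 79.5% with 101 against 81.

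**Completion proportion.** Assume that 90% complete the systemic protocol and that 20%, independently, are not packed. Completion is 90% if packing does not count and 0.90 × 0.80 = 72% if it does. Time in range (Section 5.4) is measured by bladder temperature and is defined without reference to packing.

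**The case against.** The strongest reply is that the text can be reconciled. Section 13 describes a violation as a failure to meet significant protocol requirements. What Section 8.3 requires is packing where feasible, so leaving an unpackable kidney unpacked is not a failure. The word systemic in the inclusion sentence and the listing of local cooling as a covariate both suggest that unpacked patients were meant to stay in. This is a sensible reading and probably the intended one. But the Section 13 item has no qualifier and the exclusion sentence has no exception, so the text does not secure it. Section 15 promises a detailed statistical analysis plan before the final analysis. That is a natural place for the repair, but the promise does not settle the rule.

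Four stronger readings are tempting, and the documents do not support them.

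- A reader might infer that per-protocol exclusions fall on the hypothermia arm alone. That is true of this item only. Early termination, early device removal, loss of target temperature and eligibility failures can occur in either arm.
- Read literally, the item would remove every control, since controls are never packed. Packing appears only under the experimental treatment, so this is plainly not meant.
- A reader might infer that the per-protocol result is distorted in favour of hypothermia. That needs unpacked patients to carry higher AKI risk, on which the documents are silent.
- A reader might infer that the trial cannot answer its feasibility question. Time in target range still answers part of it, and nothing links the Section 13 violations to the completion proportion.

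**Conclusion.** The concern holds as a contradiction in a stated rule. Sections 8.3, 13 and 15.3 together do not determine whether a correctly treated but unpacked hypothermia patient belongs in the per-protocol analysis of the primary endpoint. Following the exclusion sentence would apply a criterion set after randomisation to one arm only, and that comparison could be biased. Size and direction cannot be stated from the documents, because they rest on the assumed f and d; the illustrations run from no shift to several points either way.

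The intention-to-treat comparison is untouched, and so is the sample size of 101 per arm. The feasibility issue is narrower: one of the two measures lacks a definition. The point is worth correcting because the per-protocol analysis is a named analysis of the primary endpoint, but it does not threaten the trial's main conclusion.

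**What to change.** Reconcile Sections 3.2, 8.3, 13 and 15.3 before outcome data are examined by arm:

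- **Section 13:** state that not packing when packing is infeasible, which Section 8.3 allows for, is not a violation that removes a patient from the per-protocol set.
- **Section 15.3:** state that completion of the systemic temperature protocol, judged by the same criteria in both arms, governs per-protocol membership. Reword the exclusion sentence to agree with this.
- **Delivery of local cooling:** record packing in the hypothermia arm as done, infeasible, or omitted although feasible, and report the three counts descriptively. Keep the last two apart, because the condition in Section 8.3 covers only the infeasible cases.
- **Section 3.2:** state that the completion proportion refers to the systemic protocol, and report the proportion packed separately.

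The cost is wording plus one three-level item on the case report form where it is not already captured. The downside is that the per-protocol hypothermia arm will include some patients without local cooling. Common criteria will not make exclusions equal between arms: hypothermia stopped because of coagulopathy, for example, remains specific to one arm. Exclusions should therefore be tabulated by arm and reason.

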14 DATA SAFETY MONITORING

A Data Safety Monitoring Board (DSMB) has been established to review data relating to safety and efficacy, to conduct and review interim analyses, and to ensure the continued scientific validity and merit of the study. Interim reviews will be conducted by the DSMB for the purpose of monitoring study conduct and assessing patient safety at a minimum of every 6 months during the trial. Further details regarding the timing and content of the interim reviews is included in the statistical section below.

15 STATISTICAL METHODS AND CONSIDERATIONS

Prior to the analysis of the final study data, a detailed Statistical Analysis Plan (SAP) will be written describing all analyses that will be performed. The SAP will contain any modifications to the analysis plan described below.

15.1 Data Sets Analyzed

All eligible patients who are randomized into the study and receive the study treatment will be included in the safety analysis.

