 - Defined as significant bleeding that is not attributable to vascular injury in the presence of ongoing severe clinical coagulopathy despite aggressive treatment (fresh frozen plasma 15 mL/kg, cryoprecipitate 10 units x 2 doses, and the administration of antifibrinolytics). While coagulopathy is a clinical diagnosis during LTx, we would consider persistent INR > 4 or fibrinogen < 75 mg/dL after the aggressive treatment above as laboratory evidence of severe coagulopathy.
 - Severe upper gastrointestinal (GI) bleeding at the time of ECD insertion
 - It is common to have mild upper GI bleeding after insertion of a standard orogastric tube during liver transplant, so only blood return of > 500 mL will be considered an AE.
 - Severe hypothermia
 - \circ < 33 °C for greater than 30 minutes
 - Oropharyngeal, dental, or esophageal trauma
 - Perforation or damage to the ECD
 - Intraoperative cardiac arrhythmias requiring treatment ³¹ excluding bradycardia typically seen at the time of reperfusion of the liver graft.

- Intraoperative myocardial ischemia or infarction.
- Discomfort (oropharyngeal pain, dysphagia, odynophagia) patients will be asked about these symptoms post-operatively
- Surgical site infections (SSIs) prior to discharge from the hospital after LTx, or within two weeks of LTx (whichever comes first).³⁸

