10 EVALUATIONS BY VISIT

10.1 Visit 1 (Day 1, before and during LTx)

- 1. Review the study with the subject (subject's legal representative) and obtain written informed consent and HIPAA authorization and assent, if appropriate.
- 2. Assign the subject a unique screening number.
- 3. Record demographics data.
- 4. Record medical history, including a history of acute kidney injury, ascites, or hepatic encephalopathy, including diagnosis date, and prior treatments (dialysis, continuous renal replacement therapy (CRRT), large volume paracentesis).
- 5. Record concomitant medications.

- 6. Perform a complete physical examination.
- 7. Perform and record vital signs.
- 8. Perform and record oximetry.
- 9. Perform and record results of blood pressure testing.
- 10. Randomize subject (see Section 8.1).
- 11. Place ECD after induction of general anesthesia.
- 12. Implement intraoperative temperature protocol according to randomization (see Section 8.3).
- 13. Collect blood for ABGs (see Section 9.2) and NGAL determination (Section 9.3.1).
- 14. Collect urine for NGAL determination (see Section 9.3.2).
- 15. Remove ECD at the end of surgery.
- 10.2 Visit 2 (Follow-up prior to hospital discharge, window of 2 ± 1 weeks after LTx)
- 1. Record any Adverse Experiences.
- 2. Record changes to concomitant medications.
- 3. Perform complete physical examination.
- 4. Perform and record vital signs.
- 5. Perform and record oximetry.
- 6. If surrogate consent was obtained for the subject, and subject has now regained capacity, re-consent the patient for use of study data.

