12 DISCONTINUATION AND REPLACEMENT OF SUBJECTS

12.1 Early Discontinuation of Study Treatment

A subject may be discontinued from study treatment at any time if the subject, the investigator, or the surgeon feels that it is not in the subject's best interest to continue. The following is a list of possible reasons for study treatment discontinuation:

- Subject withdrawal of consent
- Adverse event that in the opinion of the investigator would be in the best interest of the subject to discontinue study treatment
- Protocol violation requiring discontinuation of study treatment

If a subject is discontinued from treatment due to an adverse event, the subject will be followed and treated by the Investigator until the abnormal parameter or symptom has resolved or stabilized.

Subjects will also be discontinued from the study treatment if the study doctor is unable to place the ECD after three attempts.

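### The safety set is worded so that it can omit randomized patients whose device placement was attempted but failed, and treated patients later found ineligible

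*Combined protocol and SAP*

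**What the plan says.** Section 15.1 contains one sentence on analysis sets: "All eligible patients who are randomized into the study and receive the study treatment will be included in the safety analysis". It sets three conditions: eligibility, randomization and receipt of study treatment. Receipt is not defined there or elsewhere.

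Section 12.1 covers failed insertion: "Subjects will also be discontinued from the study treatment if the study doctor is unable to place the ECD after three attempts".

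The listed adverse events in Section 5.3 E include two that arise from placing the device: "Severe upper gastrointestinal (GI) bleeding at the time of ECD insertion" (counted when blood return exceeds 500 mL) and "Oropharyngeal, dental, or esophageal trauma".

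Section 13 names "Failure to meet inclusion/exclusion criteria" among the protocol violations. It says violations are handled by intention-to-treat (ITT) and do not require the subject to be withdrawn.

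**The concern.** A safety set should contain everyone exposed to the risks being reported. Exposure to insertion injury begins with the first attempt to pass the device, not with the temperature protocol that follows. A set that depends on an undefined receipt of treatment lets a later analyst leave out a patient who had three failed attempts, together with any injury those attempts caused.

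The eligibility condition acts as a second filter. A patient who was cooled or warmed under protocol and is afterwards found to breach a criterion was exposed like any other, yet the wording allows that patient to be removed.

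What is at stake is the reported absolute rate of device harm. Section 2.1 names the ECD as one of the two sources of study risk, raises bleeding from varices as a theoretical possibility, and expects discomfort to be rarer than after an echocardiography probe. The safety analysis is where those expectations are tested.

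**Working it through.** The plan states no figure on this point, so the check is mainly a comparison of sections.

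**1. Order of events.** Section 10.1 lists randomization as step 10, "Place ECD after induction of general anesthesia" as step 11, and the temperature protocol as step 12. A placement failure therefore occurs after randomization and, in the listed order, before the temperature protocol.

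**2. What the treatment is.** The synopsis describes the test treatment as "Mild hypothermia (34-35 °C) during liver transplantation", which is a temperature regimen. No section says that an insertion attempt alone counts as receiving it.

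**3. Applying the conditions.**

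| Patient | Eligible | Randomized | Received treatment | Safety set (15.1) | ITT set (15.3) |
|---|---|---|---|---|---|
| Three failed placements | yes | yes | undefined | can be left out | in, unless withdrawn |
| Treated, later found ineligible | no | yes | yes | can be left out | in, unless withdrawn |

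The ITT set in Section 15.3 takes all randomized patients who were not withdrawn, with no eligibility or receipt condition. The safety set can therefore be narrower than the efficacy set.

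**4. Does another section repair this?**
- Sections 12.4 and 13 send early discontinuations and violations to ITT, but ITT is defined only in Section 15.3, for the primary endpoint.
- Section 15.4 tabulates adverse events by group and gives no other denominator.
- Section 15.6 says some subjects unable to complete the protocol will be withdrawn, which makes the status of a failed placement less clear.
- Section 15 promises a detailed SAP before final analysis; the available text contains no revised definition.

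**5. Illustration of size.** The documents give no rate of failed placement, of later ineligibility, or of injury among such patients. Everything here is assumed except the 230 planned subjects and the expectation in Section 15.5.2 that fewer than 5% have a severe or life-threatening listed event.

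- Patients left out at an assumed 1%, 3% or 5%: 230 × 0.01 = 2.3; 230 × 0.03 = 6.9; 230 × 0.05 = 11.5. That is about 2, 7 or 12.
- Ceiling on expected patients with an event: 0.05 × 230 = 11.5, so at most 11, or 11/230 = 4.78%.
- If k patients are left out and e of them had an event, the reported rate is (11 − e)/(230 − k).

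| Left out (k) | e = 0 | e = 2 | Fall when e = 2 |
|---|---|---|---|
| 2 | 11/228 = 4.82% | 9/228 = 3.95% | 0.84 point |
| 7 | 11/223 = 4.93% | 9/223 = 4.04% | 0.75 point |
| 12 | 11/218 = 5.05% | 9/218 = 4.13% | 0.65 point |

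The rate falls only when the omitted patients have events more often than 11/230. Choosing e = 2 implies event rates of 2/2 = 100%, 2/7 = 29% or 2/12 = 17% among them, and nothing in the documents supports any of these. The 5% ceiling also covers all events in Section 5.3 E, including arrhythmia, ischemia and surgical site infection. The table shows how the definition works; it is not an estimate.

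**The case against.** **Placement may already be treatment.** Section 8.3, which describes the two treatments, opens with connecting, testing and placing the ECD. Section 12.1 speaks of discontinuing treatment, which suggests that it had begun. Standard cooling and warming measures need no ECD, and no section says they must wait for it. This stands: exclusion is one reading of Section 15.1, not its only meaning. It does not settle the matter, because no section states that reading for the safety set.

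**Eligible may only describe who is enrolled.** Sections 4.1 and 8.1 say that only patients meeting the criteria enter and are randomized, and no section describes a retrospective eligibility filter. This is a fair reading. But Section 13 foresees eligibility failures among enrolled subjects, and the word as written allows their removal.

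**Three stronger readings are tempting, and the documents do not support them.**
- A reader might infer that the safety stopping rule is biased. Section 15.5.2 words that rule on all study subjects or either arm, not on the Section 15.1 set, and serious events are collected from consent (Section 11.2.1). If the monitoring board did use the 15.1 set, then with an assumed 115 per arm, 12/115 = 10.4% exceeds the 10% limit, while omitting one failed-insertion patient with an event gives 11/114 = 9.6%, which does not. The documents do not state that link.
- A reader might infer a biased comparison between arms. Both arms receive the ECD, and nothing indicates that placement failure differs by arm.
- A reader might take failed placements to be the patients most likely to be injured. That is a reasonable inference, but no figure in the plan bears it out. The only insertion-related rate given, 0.1% painful swallowing after an echocardiography probe (Section 2.1), concerns discomfort, not severe injury.

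**Conclusion.** The point holds in limited form. As worded, Section 15.1 can leave out randomized patients who were instrumented without success and treated patients later found ineligible, and no other section repairs this for the safety analysis. The consequence is a possible understatement of the absolute device-injury rate in the reported safety results. It depends on two conditions: that an analyst takes the literal reading, and that the omitted patients have more events than those kept. The size cannot be determined from the documents. Adverse events are still recorded throughout the study (Section 9.1.6), so the gap lies in the analysis set, not in data collection. The promised SAP could close it, which lowers the urgency, but the present text leaves it open.

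**What to change.** Replace the sentence in Section 15.1 with a definition based on exposure: the safety set is all randomized patients in whom ECD placement was attempted or temperature management was started, whether or not placement succeeded and regardless of any later finding on eligibility. These patients are analysed by the temperature protocol received, or by assigned arm if none was delivered. State in Section 15.5.2 that the safety stopping rule uses the same denominator, so that the report and the monitoring board work from one population.

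The cost is one sentence in Section 15.1 and a cross-reference in Section 15.5.2. No new data are needed. Reported adverse event rates may be slightly less favourable.
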